1.2 Compliance Statement

This study will be conducted in full accordance all applicable Children's Hospital of Philadelphia Research Policies and Procedures and all applicable Federal and state laws and regulations including 45 CFR 46. All episodes of noncompliance will be documented.

The investigators will perform the study in accordance with this protocol, will obtain consent and will report unanticipated problems involving risks to subjects or others in accordance with The Children's Hospital of Philadelphia IRB Policies and Procedures and all federal requirements. Collection, recording, and reporting of data will be accurate and will ensure the privacy, health, and welfare of research subjects during and after the study.

2 STUDY OBJECTIVES

We propose a longitudinal study design to determine whether 12 weeks of treatment with ivacaftor results in improvement in sleeping energy expenditure (SEE), growth status as BMI Z score, and gut health and function in n=18 children ages 6 months to 2 years with at least one CFTR gating mutation. We anticipate that these changes will accompany meaningful improvements in dietary intake, growth status and growth velocity, and serum fat soluble vitamins, bile acids and serum calprotectin in these young children.

2.1 Primary Aims

H1: Ivacaftor treatment will result in a significant reduction in SEE as percent predicted over 12 weeks compared to baseline, thereby increasing the energy available for weight gain and physical activity.

H2: Ivacaftor treatment will result in significantly increased BMI Z score over 12 weeks compared to baseline.

2.2 Secondary Aims

H3: Ivacaftor treatment will result in significantly improved gut health and function resulting in better dietary fat absorption as indicated by increased total plasma fatty acids and fecal elastase and decreased fecal calprotectin over 12 weeks compared to baseline.To determine if treatment with Ivacaftor results in increased dietary fat absorption using three methods:

2.3 Exploratory Aims

- 1) To determine the impact of ivacaftor treatment over 12 weeks compared to baseline in:
 - a) Dietary intake of calories and percent calories from fat
 - b) Growth status for length, weight, head circumference and growth velocity
 - c) Serum fat soluble vitamins A, D, E and K, bile acids, and calprotectin

3 INVESTIGATIONAL PLAN

3.1 General Schema of Study Design

3.1.1 Screening Phase

Subjects (n=18) will be recruited to participate in the study from a pool of subjects with at least one CFTR gating mutation. Given our previous success in enrolling subjects with CF from both local CF Centers and more distant Centers who traveled considerable distances to participate in our research protocols, we expect that enrollment will be achieved in a timely fashion. The plan to initiate treatment and the clinical eligibility for treatment is determined by the subject's family and the CF care team.

Potential subjects will be screened using the protocol inclusion and exclusion criteria. The CF Centers around the country and Canada will provide the study with resources that will aide in recruitment efforts (i.e. to help to identify subjects with "gating" mutations). The subject's CF care team will be contacted to confirm eligibility for the study and this will include obtaining medical information from the team and subject's medical record. To collect medical data for screening purposes, a verbal or in person consent from parents/guardians will be obtained.

Parental/guardian permission (informed consent) will be obtained prior to any study related procedures being performed.

3.1.2 Study Enrollment Phase

Eligible subjects will be enrolled into the study and come to CHOP for the study visits. Refer to Table 1 for list of assessments and the study timeline for the pace of recruitment.

3.1.3 Follow-up Phase

Their initial baseline visit (Visit 1) will occur before clinically prescribed ivacaftor treatment has begun. The exact date of the start of medication will vary for families as they obtain

their medication. Subjects will return to CHOP for the 6 week visit (Visit 2) and the 12 week visit (Visit 3 and final) after subject/family has confirmed the timing of the start of ivacaftor treatment. There may be a delay between the baseline visit and the 6 week visit based upon when treatment begins. For most families, the total duration of the study will be from 4 to 6 months. The duration of the study from start of ivacaftor treatment until last study visit will be 12 weeks. For each of the 6 and 12 week visits following the start of ivacaftor treatment, there will be a window of ±2 weeks for the visit to occur (i.e. 6 week visit may occur between 4 and 8 weeks, and 12 week visit between 10 and 14 weeks post ivacaftor treatment).

Refer to Table 1 for list of assessments and the study timeline for the visit schedule.

3.2 Study Duration, Enrollment and Number of Sites

3.2.1 Duration of Study Participation

The study duration for subject participation from enrollment to the last study visit will range from 4 to 6 months. The baseline visit will occur prior to the start of ivacaftor treatment. From the start of the clinically prescribed ivacaftor treatment to the last study visit will be 12 weeks with a window of ± 2 weeks.

3.2.2 Total Number of Study Sites/Total Number of Subjects Projected

The study will be conducted at one investigative site in the United States.

Recruitment will stop when 18 subjects are enrolled. It is expected that 18 subjects will be enrolled to produce 16 evaluable subjects.

3.3 Study Population

3.3.1 Inclusion Criteria

- Cystic fibrosis with at least one CFTR gating mutation of these ten (G551D, G178R, S549N, S549R, G551S, G1244E, S1251N, S1255P, G1439D, or R117H).
- Age: 6 months to 2 years of age
- In their usual state of good health
- A clinical decision has been made for subject to begin ivacaftor treatment.
- Family committed to the 4 to 6 month study protocol with visits to CHOP that will last 2-3 days for the baseline visit (Visit 1) prior to ivacaftor treatment and the 12 week visit (Visit 3) after clinically prescribed ivacaftor treatment has begun, and will last up to 2 days for the 6 week visit (Visit 2) after ivacaftor treatment has begun.
- Note that ivacaftor is now approved by the FDA for 6 month to 2 year old children for the additional 28 CFTR mutations known to be responsive to ivacaftor potentiation, these will also be considered. With our limited sample size, the mutations that have shown the strongest improvement with treatment will be given priority for enrollment.

3.3.2 Exclusion Criteria

- On parenteral nutrition
- Use of any inhibitor or inducer medications of cytochrome P450 (CYP) 3A
- Liver function tests elevated above 3x the reference range for age and sex
- Other illness affecting growth or nutritional status
- Other contraindications described for ivacaftor therapy

4 STUDY PROCEDURES

4.1 Screening

Subjects will be screened using the protocol inclusion and exclusion criteria. Written (in person) or verbal (via phone) parental/guardian permission will be obtained prior to scheduling any study screening related procedures. Informed written consent will be obtained at the baseline visit prior to conducting any research procedures.

All subjects will be enrolled in their usual state of good health defined as no hospitalizations, emergency room or unscheduled acute illness clinic visits, and with activity levels and food intake considered typical by the subject and their care provider for two or four weeks prior to the baseline visit.

4.2 Observational Period

Many of the protocol assessments could occur on any of the visit days (i.e. questionnaires, spot stool sample). Below is the best estimate of how each day will proceed. The baseline (Visit 1) and the 12 week (Visit 3) visit after ivacaftor treatment has begun are nearly identical with the exception of obtaining informed consent which will occur at Visit 1 Day 1 prior to any assessments being done or specimens being collected. For the 6 week (Visit 2) and 12 week (Visit 3) visits that will occur after confirmation of the timing of the start of clinically prescribed ivacaftor treatment, there will be a ± 2 week window for the visit. (i.e. 6 week visit may occur between 4 and 8 weeks, and 12 week visit between 10 and 14 weeks post ivacaftor treatment).

The description provided here applies to subjects who are not local to CHOP and who will be traveling to Philadelphia from other regions of the US and Canada and staying at a local hotel for one or two nights depending on the time of their scheduled research procedures. For non-regional families, Day 1 of each Visit is the day of arrival to CHOP and first night of their hotel stay.

If the subject is local to CHOP, we will still require a Day 1 visit for in-person written consent for Visit 1, however, for Visits 2 and 3, Days 1 and 2 can be combined to complete study protocol procedures, and they will come in to CHOP from home for the major study protocol days: Day 2 for Visit 2 and Day 2 and again on Day 3 (if needed) for Visit 3.

• •	Informed Consent/Assent will be completed in at CHOP Main CHPS Instructions in preparation for study procedures will be given Spot stool sample will be collected for Fecal Elastase I and fecal calprotec (collected anytime)
•	Questionnaires may occur on this day (see Day 2 for details)

4.2.1 Baseline visit (Visit 1)

- Spot stool sample for fecal elastase and fecal calprotectin (if not collected on Day 1)
- Questionnaires: Health History
- Anthropometry: Length, weight, head circumference, skinfolds, circumferences
- •

Day 3 (if needed and expected for half of subjects)

Sleeping energy expenditure test– if it was not performed on Day 2

Post Visit Follow Up

- 3-day weighed food records
- Begin clinically prescribed ivacaftor treatment after food records have been completed, and document the date that ivacaftor treatment was started

In Between Visits 1 & 2

• Maintain adverse events calendar

4.2.2 6 week visit (Visit 2) after ivacaftor treatment has begun

Day 1 Instructions in preparation for study procedures will be given Spot stool sample will be collected for Fecal Elastase I and fecal calprotectin (collected anytime) Questionnaires may occur on this day Day 2 Sleeping energy expenditure with morning nap (or afternoon nap if necessary). Time and amount of food and beverage intake will be recorded prior to the procedure. Anthropometry: Length, weight, head circumference, skinfolds, circumferences

- Blood draw for fatty acids and serum calprotectin
- Spot stool sample for fecal elastase and fecal calprotectin (if not collected on Day 1)
- Questionnaires regarding interval health history, Adherence to ivacaftor, enzymes, medications, and Adverse events

Post Visit Follow Up

- 3-day weighed food records
- Maintain adverse events calendar

In Between Visits 2 & 3

• Maintain adverse events calendar

4.2.3 12 week visit (Visit 3) after ivacaftor treatment has begun

•	Day 1 Instructions in preparation for study procedures will be given Spot stool sample will be collected for Fecal Elastase I and fecal calprotectin (collected anytime) Questionnaires may occur on this day
	Day 2
•	Sleeping energy expenditure with morning nap (or afternoon nap if necessary). Time and amount of food and beverage intake will be recorded prior to the procedure.
•	Blood draw for CBC, CMP, pre-albumin, bile acids, fatty acids, serum calprotectin, vitamin A (retinol), vitamin D (25(OH)D), vitamin E (a-tocopherol) and vitamin K (ucOC)
•	Spot stool sample for fecal elastase and fecal calprotectin (if not collected on Day 1)
•	Questionnaires about interval health history, Adherence to ivacaftor, enzymes, medications, and Adverse events
•	Anthropometry: Length, weight, head circumference, skinfolds, circumferences
	Day 3 (if needed and expected for half of subjects)

• Sleeping energy expenditure test- if it was not performed on Day 2

Post Visit Follow Up

- 3-day weighed food records
- Maintain adverse events calendar until 3-day food records are completed

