Statistical And Analytic Plan	Primary Aims: The goals of the primary aims of this study are to determine whether ivacaftor treatment improves SEE and BMI Z score. Secondary Aims: The goal of the secondary aim is to determine whether ivacaftor improves gut health and function as measured by total plasma fatty acids, fecal elastase and fecal calprotectin (ug/g stool). Analysis of efficacy for the primary and secondary outcomes will be based on change from baseline (before treatment) in SEE% predicted (Schofield), BMI Z scores, total plasma fatty acids, fecal elastase and fecal calprotectin. The differences between baseline and 12 weeks continuous outcomes will initially be compared using paired-t-tests if continuous variables are normally distributed and nonparametric tests (Wilcoxon sign rank) if they are not. Subsequently, mixed effects longitudinal models will be performed to assess change over all three time points (baseline, 6 and 12 weeks), adjusting for potential covariates such as age, sex, and adherence to treatment. Chi-squared tests will be used for comparison of categorical variables before and after ivacaftor treatment. Using similar methods, exploratory analyses will examine improvement in dietary intake of calories and fat, in growth status (weight, length, and head circumference Z scores) and growth velocity (both absolute and Z scores), serum fat soluble vitamins, bile acids, and calprotectin.
DATA AND SAFETY MONITORING PLAN	Safety will be formerly monitored weekly by the study team. The study protocol will be carried out in accordance with OHRP guidelines and requirements. SAEs that are unanticipated, serious, and possibly related to the study intervention will be reported to the study sponsor, IRB, CHPS, and members of the research and clinical teams in accordance with requirements. Anticipated SAEs or those unrelated to the study intervention will be reported to the same individuals/entities in accordance with requirements. There will be ongoing collection of data on adverse events and compliance to the treatment protocol throughout the study by research staff and which will be summarized and reviewed monthly by the study Principal Investigator and the Study Team. Out of range non-clinically significant laboratory data will be reviewed continually by the PI and the study team.

Schedule of Study Procedures & Study Timeline

Table 1: Summary of Methods			
	Pre-treatment	Post ivacaf	tor treatmen
Assessment	Baseline	6 weeks	12 weeks

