4.3 Unscheduled Visits

Due to the complexity of the study, no unscheduled visits will be permitted.

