6.2 Sample Size and Power

Sample Size and Power: This is a longitudinal study of the effects of ivacaftor treatment on outcomes before and after 12-week treatment. The sample size of 16 subjects to complete the study has been determined as adequate to have the power to test the primary outcomes of decrease in SEE percent predicted value (7% change), an increase in BMI Z score of 0.3, and secondary outcomes of measures of gut health and function; an increase in plasma total fatty acids from 8.5 to 10.5 mmol/L, an increase in fecal elastase of 120 ug/g stool, and a decrease in fecal calprotectin (-30 ug/g stool change). Using STATA, power calculations were generated, with α =0.05, for paired data (n=16) within the same sample (before and after 12 weeks of treatment) using the changes described above for the primary outcomes and secondary outcomes.

Primary outcomes: A sample size of 16 subjects results in 86% power to see a decrease of 7% in **SEE** (i.e. from 115 to 108) with a standard deviation of the change of 9%, using a paired t-test two-sided significance level. We demonstrated a change of similar magnitude in REE in 24 subjects with CF gating mutation after 3-mo treatment with ivacaftor^{7,9}. For growth status, 16 subjects will provide 85% power to detect an increase in **BMI Z score** of 0.3 with a standard deviation of 0.4. In the KIWI study of 2 to 5 year old children with CFTR gating mutation treated with ivacaftor for 24 weeks, a BMIZ score increase of 0.4±0.4 was demonstrated⁶. We showed a BMI Z score increase over 12 weeks of 0.3±0.4 in our recent study of 18 children (5 to 19 years) with 12-week ivacaftor treatment⁷.

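### Section 6.2 counts all 16 completers as SEE pairs for H1, but makes no allowance for a sleeping test that is still missing after Day 3, and its 86% is not what the named paired t-test gives

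*Combined protocol and SAP*

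**What the plan says.** - **Outcome and test.** H1 (section 2.1) is a "significant reduction in SEE as percent predicted over 12 weeks compared to baseline". The synopsis (Statistical and Analytic Plan) sets the order of analysis: "The differences between baseline and 12 weeks continuous outcomes will initially be compared using paired-t-tests", or the Wilcoxon signed rank test if the data are not normal. A mixed model over baseline, 6 and 12 weeks follows. Section 6.1.1 has the same sequence.
- **Measuring SEE.** In section 4.2.3, SEE at 12 weeks is done on Day 2 during a morning nap, or an afternoon nap if needed. If it was not done then, there is a further day: "Day 3 (if needed and expected for half of subjects". The same line stands under the baseline visit in section 4.2.1. Section 9.6 says that the 6-week visit has no extra-day option.
- **Later attempts.** Section 4.3: "Due to the complexity of the study, no unscheduled visits will be permitted". Section 1.1 assumes that two thirds of the children travel from other centers.
- **Power.** Section 6.2: "A sample size of 16 subjects results in 86% power to see a decrease of 7% in SEE", with an SD of the change of 9, "using a paired t-test two-sided significance level". BMI Z score is powered on the same 16.
- **Allowance for loss.** Section 6.2 plans for up to 12% attrition. Section 3.2.2 enrolls 18 to obtain 16 evaluable children, without defining evaluable. No section says how a missing SEE is handled.

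**The concern.** A child can attend all three visits and still have no usable SEE at baseline or at 12 weeks. That child counts toward BMI Z score, which needs only length and weight, but drops out of the paired test for H1. The number of pairs for H1 can therefore be smaller than the number of completers, and section 6.2 treats the two as equal. The 12% allowance has no evident room for this: 18 × 0.88 = 15.8, so attrition at the planned rate already brings 18 down to 16.

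Two things are at stake. One is the stated power for a primary outcome. The other is who is analyzed: children who cannot be tested asleep within the available days may differ from those who can, and the paired test discards whatever SEE values they do have. With two analyses planned on different sets of children and neither named as decisive, the choice between them could be made after the results are known.

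**Working it through.** **Inputs.** From section 6.2: difference 7, SD of change 9, n = 16, two-sided α = 0.05. From sections 4.2.1 and 4.2.3: half of children expected to need Day 3. Not in the documents: the share q of those children whose SEE also fails on Day 3. Assumption: q from 0% to 50%.

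**Step 1. Reproduce the 86%.** Normal approximation: power = Φ(7√n/9 − 1.960). At n = 16 this is Φ(3.111 − 1.960) = Φ(1.151) = 87.5%, within 2 points of 86%. The other four stated powers in section 6.2 (85, 80, 88 and 85%) are also within 2 points of this approximation (85.1, 81.5, 89.2 and 85.1%). The two-sided paired t-test gives 80.1, 76.1, 84.8 and 80.1% for them.

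**Step 2. The named test.** With n − 1 degrees of freedom and noncentrality 7√n/9, n = 16 has noncentrality 3.111 and critical value 2.131. Power is 82.8%. No SEE has been lost at this point, so about 3 points of the gap from 86% is calculation method.

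| Pairs | Paired t | Normal approximation |
|---|---|---|
| 16 | 82.8% | 87.5% |
| 15 | 80.0% | 85.4% |
| 14 | 76.7% | 82.9% |
| 13 | 73.1% | 80.1% |
| 12 | 69.0% | 76.9% |

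**Step 3. From Day 3 failure to pairs.** Share without SEE at one visit: m = 0.5q. If baseline can fail in the same way, independently, the share without a pair is 1 − (1 − 0.5q)². Paired t power is averaged over the binomial number of pairs from 16 children.

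| q (assumed) | 12 weeks only: missing, mean pairs, power | Baseline and 12 weeks: missing, power |
|---|---|---|
| 0% | 0%, 16, 82.8% | 0%, 82.8% |
| 10% | 5%, 15.2, 80.4% | 9.8%, 77.9% |
| 25% | 12.5%, 14, 76.4% | 23.4%, 69.3% |
| 50% | 25%, 12, 68.2% | 43.8%, 52.7% |

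The loss due to missing 12-week SEE alone is thus 82.8 − 80.4 = 2.4 points at q = 10% and 82.8 − 68.2 = 14.6 points at q = 50%.

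**Step 4. What the mixed model recovers.** An SD of change of 9 implies a residual variance of 81/2 = 40.5. Between-child variance is assumed to be 23.5 to 64; 64 is the square of the SD of 8 that section 6.2 cites for healthy one-year-olds, and 64 − 40.5 = 23.5. With 16 children, all with baseline SEE and half without a 6-week SEE, the standard error of the 12-week contrast is:
- 25% missing at 12 weeks: about 2.5, against 9/√12 = 2.60 for the paired test.
- 10% missing: about 2.34, against 9/√14.4 = 2.37.

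**The case against.** The strongest reply is that the plan never says SEE will fail on Day 3. It gives only the share expected to need that day, and section 9.6 treats the extra day as the one on which procedures are completed. That points to a q near zero. Nor does a test not done on Day 2 have to be a failed nap: section 4.2 calls the daily schedule a best estimate and links hotel nights to the timing of procedures. This stands. A reader might infer that the plan's own figures put a quarter of children without a 12-week SEE. They do not: 25% needs a second, independent 50% failure that appears nowhere in the documents.

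It is also fair to say that evaluable might be meant to include having SEE, and that section 6.2 says enrolling 18 leaves room for greater variability. If nobody withdrew, 18 pairs would give 87.5% by the paired t-test. But the documents do not say that the margin covers failed tests, and planned attrition would use it up.

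Finally, the mixed model is already planned, so a child without a 12-week SEE is not lost to every analysis, and the gain in precision is small. Both are correct. The case for making it decisive rests mainly on keeping those children in and on settling the choice in advance.

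**Conclusion.** The point holds as a gap in the plan with a conditional cost. What is certain: H1 needs SEE at both visits, section 6.2 equates pairs with completers, there is no rule for a missing SEE, and the named test gives 82.8% rather than 86% with all 16 pairs present.

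What is conditional is the further loss. It runs from nothing at q = 0% to about 15 points at q = 50% when only 12-week SEE can fail, and is larger if baseline SEE fails as well. These figures rest on 16 children attending at 12 weeks, the plan's difference of 7 and SD of 9, and failures independent across days and visits.

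A reader might also infer that failed naps alone take power from 86% to 68%. That compares two methods of calculation. The like-for-like figure is 82.8% to 68.2%, and only at the assumed upper bound. On the normal approximation, losing one pair still leaves 85.4%. A failure of H1's power because of failed sleeping tests is therefore not demonstrated.

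**What to change.** 1. **Section 6.2.** Separate the number completing from the number with a usable SEE at both baseline and 12 weeks. Define evaluable for H1, state the expected share of missing SEE, and give H1 power by the two-sided paired t-test for 12 to 16 pairs (69.0% to 82.8%).
2. **Section 6.1.1.** Name the already planned mixed model as the analysis that decides H1: visit as a category, all available SEE values, the 12-week contrast against baseline, covariates fixed in advance, and a small-sample degrees-of-freedom method. Keep the paired test as support.
3. **Reporting.** Give the number without a usable SEE at each visit. The 6-week visit matters here, because it has no extra day and its values are what the model uses for a child without a 12-week SEE.

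The cost is wording and a less favorable stated power; no visits or children are added. The model relies on SEE being missing at random given the observed values. That cannot be verified, but it is weaker than the paired test's assumption that excluded children resemble the rest. The precision gain is small, as shown above, and should not be presented as restoring the lost power.
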